9.4.3.1 Lesion Total Sign Score (TSS)

Main comparison for TSS will be the comparison between PRN473 Gel, 5% and placebo for change from Baseline to Day 15.

Change in TSS will be analyzed with a linear mixed effects model with fixed terms for treatment and with baseline TSS as a covariate

Change in TSS = baseline TSS + treatment + error

and with an unstructured matrix of treatment variances and covariance for patient, using SAS Proc Mixed[®]. In case of convergence problems, other variance-covariance structures will be explored. Baseline TSS will be defined as the mean TSS from the two treated lesions at baseline.

The 95% Confidence Interval (CI) for the treatments effect will be obtained for the difference between treatment means within the linear mixed effects model framework. Additionally, 80% CIs will be derived and presented.

Descriptive statistics and graphical displays will be provided for all timepoints.

Additional explorative analyses may be performed.

9.4.3.2 Further efficacy endpoints during the blinded period

Further efficacy endpoints during the blinded period will be summarized per treatment and timepoint:

- Change from Baseline in daily lesional PP-NRS score up to Day 15
- Change from Baseline in lesional validated IGA score at Days 8 and 15
- Lesional validated IGA response (proportion of patients with a validated IGA score of 0 or 1 and ≥2-grade improvement from Baseline) at Days 8 and 15

Further explorative analyses may be performed.

9.4.3.3 Eczema Area and Skin Severity Index (EASI)

The following endpoints will be derived and analysed:

- Change from Baseline in EASI at Days 29 and 43
- Change from Day 15 in EASI to Days 29 and 43
- Proportion of patients with EASI 50, EASI 75, and EASI 90 from Day 15 to Days 29 and 43

Changes in EASI from Day 15 to Day 29 and to Day 43 will be analyzed descriptively. Estimations with 95% and 80% CIs may be derived. Descriptive statistics and graphical displays will be provided per timepoint.

Frequency tables will be provided for EASI 50, EASI 75, and EASI 90.

Further explorative analyses may be performed.

9.4.3.4 Validated Investigator Global Assessment-Atopic Dermatitis (vIGA-AD)

The proportion of patients achieving at least 2 grade reduction in vIGA-AD to clear (vIGA-AD 0) or almost clear (vIGA-AD 1) from Day 15 to Days 29 and 43 will be summarized.

Further explorative analyses may be performed.

Product Name: PRN473 (SAR444727)

9.4.3.5 Further efficacy endpoints during the open-label period

Further efficacy endpoints during the open label period will be summarized per timepoint:

- Change from Baseline in TSS for the 2 target lesions at Days 29 and 43.
- Change in PP-NRS from Day 15 to Days 29 and 43
- Proportion of patients achieving at least 3-point reduction from Day 15 in PP-NRS at Days 29 and 43
- Proportion of patients achieving at least a 4-point reduction from Day 15 in PP-NRS at Days 29 and 43
- Change from Day 15 in weekly mean of PP-NRS at Days 29 and 43
- Change from Day 15 in SCORAD at Days 29 and 43
- Change from Day 15 in percentage of treatable BSA at Days 29 and 43
- Change from Baseline in POEM at Days 15, 29, and 43
- Change from Baseline in DLQI at Days 15, 29, and 43

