- The EASI, the POEM, and the DLQI will be performed predose at Baseline (Day 1), Days 15 and 29, and at End of Study/Early Termination visit (Day 43).
- The vIGA-AD (Appendix 4, Section 10.4.2) will be performed, predose at Days 15 and 29, and at End of Study/Early Termination visit (Day 43).
- The SCORAD will be performed predose at Days 15 and 29, and at End of Study/Early Termination visit (Day 43).

- The PP-NRS will be administered daily predose before patient morning application during the Open-Label Period (Days 15-42) and at End of Study/Early Termination visit (Day 43).
- The percentage of treatable BSA will be calculated at Screening, Days 15 and 29, and at End of Study/Early Termination visit (Day 43).

To be included in the population analyzed for efficacy, the patient must have received at least 80% of prescribed study intervention in the Blinded Period and/or at least 80% of prescribed study intervention in the Open-Label Period.

Skin tape stripping (STS) will be performed predose on Days 1, 8 (optional), 15, 29, and at Day 43 for the two target lesions and on Day 1 for the normal skin. For a minimum of 20 patients (may be reduced to 15 patients if there is an impact on enrollment from COVID-19, a 4 or 5 mm punch skin biopsy will be collected from each target lesion on Days 1, 15, and 29 (optional) and from normal skin on Day 1. The lesional biopsy specimens at Days 15 and 29 will be collected in the vicinity of the Day 1 (Baseline lesional sample) biopsy but must be at least 1 cm away from the prior biopsy site. If the target lesion cleared after Day 1 and before Day 15, the biopsy specimen will be taken from the lesional skin location of the target area identified at Baseline.

Additional information regarding study assessments and their timing is located in the Schedule of Activities (Section 1.3).

Inclusive of an up to 5-week screening period, a 6-week treatment period, end of study assessments 1 day after last dose, and a safety follow-up phone call 2 weeks after last dose, the participation will take approximately 13 weeks.

Due to the COVID-19 pandemic, safety measures may be implemented to ensure continued supply of study medication and safety monitoring for patients. When the COVID-19 pandemic resolves, the measures will be repealed back to the previous state as government rules and benefit/risk assessment allow.

As required, these approaches (in accordance with local regulations) will be documented in site guidance materials.

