8.1 EFFICACY ASSESSMENTS

Efficacy assessments will be performed per the Schedule of Assessments in Section 1.3:

- Lesional PP-NRS is a patient-completed assessment to determine the intensity of lesion pruritus.
- Lesional validated IGA is an Investigator assessment of the 2 target lesions during the Blinded Period and predose at D15 during the Open-Label Period.
- Eczema Area and Skin Severity Index (EASI) is a validated Investigator-administered scoring system used to measure the severity of clinical signs in AD.
- Validated Investigator Global Assessment-Atopic Dermatitis (vIGA-AD; Appendix 4, Section 10.4.2) is an Investigator assessment of the global severity of clinical signs in AD.
- Lesion TSS (Appendix 4, Section 10.4.3) is a scale that rates the severity of each of 4 AD symptoms (erythema, induration/papulation, excoriation, and lichenification) on a 4-point scale from 0 (none) to 3 (severe), for a total score ranging from 0 to 12.

- SCORing atopic dermatitis (SCORAD) is a clinical tool used to assess AD by intensity, extent, and subjective signs.
- Peak Pruritus Numeric Rating Scale (PP-NRS) is a patient-completed assessment to determine the intensity of peak pruritus over the previous 24 hours.
- Patient-Oriented Eczema Measure (POEM) is a validated, patient-derived assessment measure for monitoring atopic eczema severity.
- Dermatology Life Quality Index (DLQI) is a validated, self-administered questionnaire designed to measure the health-related quality of life of adult patients suffering from a skin disease.
- Estimation of treatable BSA.

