3.4 TERTIARY/EXPLORATORY ENDPOINT(S) ANALYSIS

There are two type of exploratory endpoints. The first exploratory endpoint is biomarker to evaluate changes in blood samples, skin tape stripplings, and skin biopsies. Details are given in [Section 3.7.1.2](#).

The second exploratory endpoints are efficacy endpoints during double-blind period and Open-label period based on the efficacy population. For the double-blind period, treatment differences or ratios will be assessed for SAR444727 Gel, 5% versus placebo at Day 8 and Day 15, and data will be presented by treatment for the blinded period, for scores assessed per lesion, and overall otherwise. During the Open-Label Period, efficacy will be assessed mainly at Days 29 and 43,

overall. For TSS, data will be described over the full course of the study presented by treatment received during the double-blind Period.

More specifically, the following endpoints will be assessed:

During double-blind period

- Change from Baseline in lesional TSS for the 2 target lesions at Day 8 and Day 15
- Change from Baseline in daily lesional Peak Pruritus Numeric Rating Scale (PP-NRS) score for the 2 target lesions up to Day 15 and at Day 15
- Change from Baseline in lesional validated Investigator Global Assessment for AD (v-IGA-AD) score for the 2 target lesions at Days 8 and 15
- Lesional v-IGA-AD response (proportion of participants with a lesional v-IGA-AD score of 0 [clear] or 1 [almost clear] and ≥ 2 -grade improvement from Baseline) at Days 8 and 15

During Open-label period

- For lesional TSS
 - Change from Baseline in lesional TSS for the 2 target lesions at Days 29 and 43
 - Change from Day 15 in lesional TSS for the 2 target lesions at Days 29 and 43
- For PP-NRS
 - Change in daily global PP-NRS from Day 15 to Days 29 and 43
 - Change in weekly average of PP-NRS from Day 15 to Days 29 and 43
 - Proportion of participants achieving at least 3-point reduction from Day 15 in daily global PP-NRS at Days 29 and 43 in participants with PP-NRS ≥ 3 at Day 15
 - Proportion of participants achieving at least a 4-point reduction from Day 15 in daily global PP-NRS at Days 29 and 43 in participants with PP-NRS ≥ 4 at Day 15
- For Eczema Area and Skin Severity Index (EASI)
 - Percent change from Baseline in EASI at Days 29 and 43
 - Percent change from Day 15 in EASI at Days 29 and 43

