Participants with missing data at Baseline will not be included in the analysis. Participants with one or more post-dose timepoints will be included. Mixed model for repeated measures (MMRM) to account for missing data is used for the primary analysis under the missing at random (MAR) framework. Parameters will be estimated using restricted maximum likelihood method with the Newton-Raphson algorithm. Denominator degrees of freedom will be estimated using Kenward-Roger adjustment. All efficacy data after discontinuation of treatment will not be considered.

The same analysis will be conducted for lesional v-IGA-AD score at Days 8 and 15 and lesional PP-NRS. For the other efficacy parameters, only descriptive analyses will be provided.

The weekly average PP-NRS scores will be defined as the average of daily non-missing scores within the week preceding the given visit and will be calculated if there is a minimal amount of 4 non-missing scores.

The POEM score is a 5-point scale: 0 (“No days”), 1 (“1-2 days”), 2 (“3-4 days”), 3 (“5-6 days”) and 4 (“Every day”). The POEM score is calculated by summing the values for the 7 items.

If two or more questions are left unanswered the questionnaire is not scored.

The DLQI is a 4-point scale: 0 (“Not relevant”/“Not at all”), 1 (“A little”), 2 (“A lot”), 3 (“Very much”). For Question 7, “Prevented work or studying” is scored at 3. The DLQI is calculated by summing the score of each question.

The EASI-50/75/95/100 response is defined as a participant achieved a decrease by at least 50%/ 75%/ 95%/100% of EASI from Day 15.

Change in lesional TSS, PP-NRS (daily global and weekly average), EASI, BSA, SCORAD, POEM, DLQI during the Open label period will be analyzed descriptively. Estimations with 95% and 80% CIs may be derived. Sub-score of EASI by localization will also be provided.

Supplemental analyses

Where appropriate, supplemental analyses may be presented excluding observations after administration of rescue medication. No imputation will be made.

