After applying these time windows, if multiple assessments are associated to the same time point, the closest from the targeted study day will be used. If the difference is a tie, the value after the targeted study day will be used. If multiple valid values exist within a same day, then the first value of the day will be selected when time is available, otherwise the scheduled exam will be used.

If there is no measurement for a given parameter in an analysis window, data will be considered missing for the corresponding visit.

Table 6 - Analyses window definition

Study period	Scheduled visit post baseline	Targeted study day	Analysis window in study days
Double blind period	Day 8	8	7 to 9
	Day 15	15	13 to 18
Open label period	Day 29	29	25 to 33
	Day 43	43	39 to 47

Study days are calculated considering Day 1 as the day of first administration of intervention in blinded period.

Unscheduled and end of treatment (EOT)/EOS visits

Unscheduled visit measurements of efficacy, laboratory data, vital signs, PK and biomarkers will be used, in particular for computation of Baseline, the last on-treatment value, analysis according to PCSAs, and the shift summaries for safety. They will also be included in the by-visit summaries if they are re-allocated to scheduled visits.

Signature Page for VV-CLIN-0634985 v1.0
act17131-16-1-9-sap

Approve & eSign

Approve & eSign

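### The open-label 3- and 4-point itch responses compare two single daily PP-NRS scores in an uncontrolled period, so day-to-day noise inflates the responder rate

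*Protocol*

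**What the plan says.** Protocol 9.4.3.5 includes the "Proportion of patients achieving at least 3-point reduction from Day 15 in PP-NRS at Days 29 and 43" and the matching 4-point endpoint. It does not say which score represents a visit and does not restrict the denominator.

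SAP 3.4 settles both. The score is the daily one, "Proportion of participants achieving at least 3-point reduction from Day 15 in daily global PP-NRS at Days 29 and 43", and the 3-point analysis covers only participants scoring at least 3 at Day 15. The 4-point analysis is done "in participants with PP-NRS ≥ 4 at Day 15". The same Day 15 score therefore defines the denominator and serves as the reference.

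Each score is a "patient-completed assessment to determine the intensity of peak pruritus over the previous 24 hours" (Protocol 8.1). Where an analysis window holds several values, "the closest from the targeted study day will be used" (SAP 5.4), so one value is kept and none are averaged.

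More data exist than these endpoints use. Protocol 4.1 states: "The PP-NRS will be administered daily predose before patient morning application during the Open-Label Period (Days 15-42"), with a further score at Day 43. SAP 3.4 also has an averaging rule: "The weekly average PP-NRS scores will be defined as the average of daily non-missing scores within the week preceding the given visit", requiring at least 4 scores. The plan applies that average only to a continuous change, not to the responses. Before Day 15 only the lesional PP-NRS, scored separately for each target lesion, is collected.

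**The concern.** A score with a 24-hour recall moves from day to day without any change in the disease. When two such scores are subtracted, both fluctuations enter the difference, and some patients cross a 3- or 4-point threshold by chance. A control arm would show how often that happens. The open-label period has none, so the chance share cannot be subtracted from the observed rate. The planned 95% and 80% confidence intervals show sampling error and do not reveal this inflation.

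What is at stake is the reading of a signal-seeking study of up to 40 patients, where a handful of chance responders is a visible part of the rate. The noise at Days 29 and 43 can be reduced with scores already being collected.

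**Working it through.** **Inputs.** From the documents: thresholds of 3 and 4 points; denominators of Day 15 score ≥3 and ≥4; daily global scores from Day 15; weekly average of the days before the visit. The plan gives no PP-NRS mean, SD or expected response rate, so it has no figure to reproduce. Assumed, and not from the documents: integer 0–10 scale, mean 5, between-patient SD 1.8, lag-1 correlation 0.3 between days, and day-to-day SD s = 1.3 (range 1.0 to 1.6). There is no true change.

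**Closed-form check at s = 1.3, single days.** Day 15 and Day 29 are two weeks apart, so their noise is practically independent.

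- SD of the difference: 1.3 × √2 = 1.84.
- On integer scores, a 3-point fall is roughly an underlying fall above 2.5. P(Z > 2.5/1.84 = 1.36) = 0.087 of all patients.
- Share with Day 15 ≥3: SD of one score = √(1.8² + 1.3²) = 2.22; P(Z > (2.5 − 5)/2.22 = −1.13) = 0.87.
- Chance 3-point responders in the SAP's denominator: 0.087/0.87 = 10%.
- 4-point: P(Z > 3.5/1.84 = 1.90) = 0.0285. Share with Day 15 ≥4: P(Z > −1.5/2.22 = −0.68) = 0.75. 0.0285/0.75 = 3.8%.

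**Weekly average at the later visit.** With lag-1 correlation 0.3, a 7-day mean has 0.24 of the one-day variance. The SD of Day 15 minus the weekly mean is 1.3 × √(1 + 0.24) = 1.45. P(Z > 3/1.45 = 2.07) = 0.019, and 0.019/0.87 = 2.2%. Rounding of the Day 15 score adds a little.

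**Simulation** (300,000 patients per setting, s = 1.3, with s = 1.0 to 1.6 in brackets, no true change):

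| Response | Single days | Weekly average at visit |
|---|---|---|
| 3-point | 9.9% (4.5–15.4%) | 2.5% (0.6–5.6%) |
| 4-point | 3.7% (0.9–7.8%) | 0.4% (0–1.6%) |

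**Sensitivity.** A second model used independent days, between-patient SD 2 and mean 4 to 6. It gave single-day 3-point rates of 0.1% at s = 0.5, 4–5% at 1.0, 12–15% at 1.5 and 19–25% at 2.0. With the weekly average at the visit the rates were about 0.4–0.5% at 1.0, 3–5% at 1.5 and 8–11% at 2.0.

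**Role of the Day 15 threshold.** A fall of 3 needs a Day 15 score of at least 3, so the restriction cannot create a responder. In the second model at mean 5 and s = 1.5, 11.4% of all patients respond by chance. With 84% of patients retained, 0.114/0.84 = 13.6%, so the increase comes from the denominator. The retained group also regresses: 13.6% improve by at least 3 points and 8.5% worsen by that much. Among all patients the two are nearly equal (11.4% and 11.5%).

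**What averaging leaves.** In the first model at s = 1.3, the mean change among patients with Day 15 ≥3 is −0.19 with single days and −0.19 with the weekly average.

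**Under a real effect (s = 1.3), single days versus weekly average:**

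| True fall, all patients | 3-point | 4-point |
|---|---|---|
| 2 points | 43% vs 28% | 25% vs 11% |
| 4 points | 83% vs 76% | 68% vs 54% |

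**The case against.** The strongest objection is that averaging costs more than it gains. At a true 4-point fall, the 4-point rate drops from 68% to 54%. The gap from the no-change rate narrows from 68 − 3.7 = about 64 points to 54 − 0.4 = about 54. For the 3-point response the gap hardly moves (83 − 9.9 = 73 against 76 − 2.5 = 73.5). Part of this is structural: a mean must reach the threshold itself, while a rounded score needs an underlying fall of only about 2.5. The cost is real and must be disclosed. It does not decide the matter, because those comparisons give every patient the same true fall. When the true fall varied between patients, the weekly-average rate was closer to the true responder rate and classified more patients correctly in every setting tried. In one setting the true rate was 24%, the single-day rate 45% and the weekly-average rate 34%.

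A second objection is that the plan already includes the change in weekly mean PP-NRS. That cannot stand in for the responses, because a Day 15 weekly mean needs at least 4 global scores from the preceding week and none are collected then.

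Third, the size rests on assumed values. That stands: across the two models the 3-point chance rate runs from 0.1% to 25%. Sampling error is also wide; 4 of 40 has a Wilson 95% interval of 4–23%.

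A reader might infer that selecting on the Day 15 score manufactures responders. The documents do not support that, since anyone excluded could not have responded. A reader might also infer that chance responders will be reported as drug effect, or that a false-positive rate is inflated. Protocol 9.1 tests no hypothesis, the period is labelled uncontrolled, and the efficacy analyses are described as early and explorative.

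**Conclusion.** The concern holds as a matter of interpretation. Both responses are classified from two single daily scores in an uncontrolled period, although daily scores and a weekly-average rule exist. With no true change, on the assumed mean of 5, between-patient SD of 1.8, lag-1 correlation of 0.3 and day-to-day SD of 1.0 to 1.6, about 5–15% of the analysed patients would be 3-point responders and 1–8% would be 4-point responders. At a day-to-day SD of 0.5 the rate is near zero. The cause is the comparison of two single days. The Day 15 restriction shrinks the denominator and leaves a group that drifts downward.

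It would go too far to claim that the weekly average cures the problem. The Day 15 reference stays a single score, so regression to the mean is untouched and about 0.6–6% of 3-point chance responders remain on the same assumptions.

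**What to change.** In SAP 3.4 and Protocol 9.4.3.5, define the 3- and 4-point responses as the Day 15 score minus the weekly average at Day 29 or Day 43, using the SAP's existing rule of at least 4 scores. Report the single-day version beside it as supportive.

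Add the proportion worsening by at least 3 points among all patients, not only those above the Day 15 threshold, to show the noise level. Without true change it matches the chance improvement rate among all patients. A real fall lowers it, so it is then only a lower guide.

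State that the Day 15 reference is a single day because no global PP-NRS is collected before it, and that regression to the mean is therefore not removed.

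**Cost.** Wording only: no new visits or data, and the weekly averages are already derived. The same endpoints in the protocol synopsis, Protocol Table 3 and SAP Table 1 need matching edits. Observed rates will be lower, including under a real effect (true 4-point fall: 3-point 83% to 76%, 4-point 68% to 54%), and the report should say so. Patients with fewer than 4 scores in the week have no weekly average, so their number should be shown.

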9.4.4 Analysis of safety data

The safety evaluation will be based upon the review of the individual values (clinically significant abnormalities), descriptive statistics (summary tables, figures) and, if needed, on statistical analysis (appropriate estimations, confidence intervals). No statistical significance tests will be performed on safety data.

Potentially clinically significant abnormality (PCSA) values are defined as abnormal values considered medically important by the Sponsor, according to predefined criteria/thresholds based on literature reviews and defined by the Sponsor for clinical laboratory tests, vital signs, and ECG parameters.

All the safety analyses will be performed based on the safety population. Where appropriate, supplemental analyses will be presented excluding observations after administration of rescue medication.

For all safety data variables, the following observation periods are defined and used for classification of AEs, determination of on-treatment PCSA values, and the last on-treatment value for laboratory and vital sign parameters:

- The pre-treatment period is defined as the time between informed consent signature and the first study intervention administration.
- The treatment-emergent period is defined as the time from the first study intervention administration through the End of Study visit.
- The post treatment period is defined as the time starting after the treatment-emergent period.

9.4.4.1 Assignment to treatment and study phase

Safety data will be assigned to study phase as following:

- Blinded Period, if the TEAE onset was between the first administration (Day 1) of any study intervention in the Blinded Period and the first administration of study intervention (PRN473 Gel, 5%) in the Open-Label Period (scheduled Day 15).
- Open-Label Period, if the TEAE onset was after the first administration of study intervention (PRN473 Gel, 5%) in the Open-Label Period (scheduled Day 15).

Adverse events which are possibly related to study intervention and have onset date after the first dose of PRN473 will be considered possibly related to PRN473, unless they are documented as possibly related to the study intervention formulation of the placebo-treated lesion and not possibly related to the study intervention formulation of the PRN473 Gel, 5%-treated lesion.

Table 8 - Safety analysis

Safety Measures	Statistical Analysis Methods	
Adverse events	Treatment-emergent adverse event incidence tables will be presented by System Organ Class, high-level group term, high-level term, and Preferred Term for each study period and overall, showing the number (n) and percentage (%) of patients experiencing a TEAE.	
 AEs leading to study intervention or study discontinuation AEs leading to death PCSAs 	Multiple occurrences of the same event in the same patient will be counted only once in the tables. The denominator for computation of percentages will be the corresponding safety population. In addition, TEAEs will be described according to maximum intensity and relation to the study intervention.	
	Adverse events that occur outside the treatment emergent period will be listed separately.	
	Proportion of patients with at least 1 TEAE, treatment-emergent SAE, TEAE leading to death, and TEAE leading to definitive treatment discontinuation will be tabulated by study period and overall.	
	The incidence of PCSAs occurring during the TE period will be summarized overall and by baseline status.	

Abbreviations: AE = adverse event; PCSA = potentially clinically significant abnormality; SAE = serious adverse event; TEAE = treatment-emergent adverse event.

